grade 3 or higher pneumonitis, grade 3 or higher nephritis, grade 3 or higher transaminitis, or any grade myocarditis in 2 out of the first 6 patients in the AML arm of the study. In this case, the upper 90% one-sided CI bound for 2 patients with SAEs within 6 patients would be 66.7%, consistent with an excessive rate of toxicity.

- The fraction of patients experiencing grade 3 or higher colitis/diarrhea, grade 3 or higher pneumonitis, grade 3 or higher nephritis, grade 3 or higher transaminitis, or any grade myocarditis exceeds 40%, at any time during study implementation beyond the first 6 patients in the AML arm.

If the study is stopped due to activation of the above rules, the safety data will be examined by the Sponsor in consultation with investigators in order to determine how to proceed or whether to discontinue the study at large.

Note: Dose modifications for HMA-related (known/expected) toxicities -for either azacitidine or decitabine- in AML patients will be based on the respective US Prescribing Information for these products. These documents are included as Appendices 12.1 and 12.2.

Procedures

After signing the informed consent, patients will enter the 28-day Screening period. At the baseline visit (Day -2), all pretreatment screening procedures/assessments must be completed, review of inclusion/exclusion criteria (including specific tumor histologic type verification, [e.g., TNBC]), and review of laboratory and tissue pathology results confirmed prior to enrollment and the first GM-CSF injection.

Patients will then enter the open-label treatment period which is approximately 111 weeks (777 days; 2.13 years) in duration; the last galinpepimut-S administration would occur at 84 weeks (day 588 days; 1.61 years).

Patients will be treated until progression, death, unacceptable toxicity (including activation of the stopping rules in either the solid tumor arms or the AML arm), or completion of 2 years of therapy with pembrolizumab, whichever occurs first.

A safety follow-up period will occur 30 days after the last administration of study drug. A follow-up phone call for serious adverse events will occur 90 days after the last dose of pembrolizumab or 30 days following cessation of study treatment if the patient begins new anticancer therapy, whichever is earlier. If the patient initiates new anticancer therapy, this must be reported by the investigator.

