3.1.1. Overall Treatment Investigational Administration Schedule

Patients will receive 70 µg sargramostim (GM-CSF) SC on Day -2 and on Day 1 before each galinpepimut-S injection. The first GM-CSF injection of each doublet will occur at the same anatomical site of the planned galinpepimut-S treatment injection within each given cycle.

The first 2 galinpepimut-S injections will initially be administered as monotherapy every 3 weeks (Week 0 and Week 3). Thereafter, galinpepimut-S will be co-administered with pembrolizumab every 3 weeks for 4 additional administrations (for the galinpepimut-S initial immunization induction phase series; weeks 6-15) to coincide with the per label pembrolizumab dosing frequency. After that, there will be one un-paired administration of pembrolizumab (week 18), and then galinpepimut-S will be resumed on an every 3-week schedule for 6 additional doses (early immune booster phase; weeks 21-36). At the end of this phase, there will be a 12-week interval where 3 unpaired administrations of

pembrolizumab will occur (weeks 39-45), and then galinpepimut-S will be resumed on an every 12-week schedule for 4 additional doses (late immune booster phase; weeks 48-84). After 84 weeks, continuing non-progressed patients will be treated with pembrolizumab alone up until week 111. Galinpepimut-S will be administered 30-60 minutes after the completion of IV infusion of pembrolizumab on Day 1 of each cycle during which the 2 drugs are being co-administered.

Pembrolizumab will be administered at a dose of 200 mg intravenously every 3 weeks on Day 1 of each cycle (3-week cycles) starting on Study Week 6 and continuing for up to 2 years thereafter (Study Week 111). To monitor for any adverse reactions, specifically for systemic anaphylaxis type reactions against either GM-CSF or galinpepimut-S, patients will remain in the clinic for approximately 30 minutes following each GM-CSF or galinpepimut-S injection. Safety assessments will be conducted at every visit. The end of treatment (EOT) visit will occur 30 days after the last injection.

Specifically for patients in the AML arm, the timing of the administration of the investigational therapies (pembrolizumab and galinpepimut-S) with respect to administration of hypomethylating agents (HMAs) will be as follows:

- AML patients on cycles #1 – 4 of HMA on-label therapy (treated according to standard clinical care) will be pre-screened to gauge potential eligibility for the study.

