 - Grade 4 is defined as ANC < 1000/mm³ with a single temperature of > 38.3°C (101°F) or a sustained temperature of ≥ 38°C (100.4°F) for more than 1 hour, with life-threatening consequences and urgent intervention indicated.
 7. Any treatment-related toxicity that causes the patient to discontinue treatment during the period from the first administration of galipepimut-S until the completion of the first cycle of galipepimut-S plus pembrolizumab combination therapy.
 8. Missing > 25% of pembrolizumab doses as a result of drug-related AE(s) during the first cycle of combination therapy.
 9. Thrombocytopenia < 25,000/mm³ if associated with:
 - A bleeding event which does not result in hemodynamic instability but requires an elective platelet transfusion, or
 - A life-threatening bleeding event which results in urgent intervention and admission to an Intensive Care Unit (ICU)
 10. Prolonged delay (> 2 weeks) in initiating Cycle 2 of combination therapy due to treatment-related toxicity
 11. Grade 5 toxicity.

Missing > 25% of the doses of either investigational agent as a result of drug-related AE(s) during the period from first administration of galipepimut-S and up until the completion of

the first cycle of the co-administration of galinpepimut-S in combination with pembrolizumab.

Staggered Early Enrollment:

To minimize exposing subjects to the risk of potential unknown acute and subacute toxicities of combining pembrolizumab with galinpepimut-S, the inter-dosing interval in-between the first consecutive three (3) subjects to be enrolled in this study arm will be one (1) week following the administration of the first dose of pembrolizumab in these patients.

DLT assessment and actions will be as follows (unless stopping rules apply):

- If 2 or fewer patients of these first 6 patients have DLTs, enrollment can continue for up to another 6 patients across these arms with no dose adjustments made. If DLTs are observed in more than 2 patients of the first 6, the time interval between galinpepimut-S doses for the inoculation following the one associated with the DLT will be doubled. For example, if galinpepimut-S was given on a Q3W schedule before the DLT occurred, it should be given Q6W for the immediately subsequent administration after the dosing event associated with the DLT, while keeping the pembrolizumab dose and frequency stable.

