- In the next 6 patients (patients 7 to 12), if again, 2 or fewer of these patients have DLTs observed, enrollment can continue. If DLTs are observed in more than 2 of patients 7 to 12, the time interval between galinpepimut-S doses for the inoculation following the one associated with the DLT will be doubled, , but pembrolizumab will continue as scheduled.
- If DLTs are observed in more than 2 patients of the first 6 (patients 1 to 6) and again in more than 2 patients of the next 6 (patients 7 to 12), the time interval between galinpepimut-S doses will be doubled for two (2) inoculations following the one associated with the DLT. For example, if galinpepimut-S was given on a Q3W schedule before the DLT occurred, it should be given Q6W for the 2 immediately subsequent administrations after the dosing event associated with the DLT, while keeping the pembrolizumab dose and frequency stable.

- If DLTs continue to be observed above 2 per every 6 patients beyond these first 12 patients, and even after the changes in administration of galinpepimut-S, the study will be stopped and the safety data will be examined by the sponsor in consultation with investigators in order to determine how to proceed or whether to discontinue the study.
- Should a given patient experience any of the above DLTs at any time after the completion of the first cycle of co-administration of galinpepimut-S in combination with pembrolizumab, the time interval between galinpepimut-S doses for the inoculation following the one associated with the DLT will be doubled, but pembrolizumab will continue as scheduled.
- If another DLT occurs in that next cycle, the time interval between galinpepimut-S doses will be doubled for two (2) inoculations following the one associated with the DLT, but pembrolizumab will continue as scheduled.
- If no DLTs re-occur after the above periods of doubly 'spaced out' administrations, then the patient should revert back to the initial GPS Q3W schedule (as per the initial dosing frequency/ investigational agent administration schedule).
- If a DLT occurs after these dose modifications in subsequent cycles, the patient will be discontinued from the study.

The above dose density modifications in response to DLTs is further summarized in the bulleted list of actions below:

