- First DLT → skip the next GPS inoculation (scheduled for the next cycle, i.e., 3 wks ahead) and administer GPS 6 wks ahead (i.e., 'spread out') **once thereafter**, i.e. **for 1 additional cycle** → DLT resolution → Return to per protocol schedule of GPS administration
- Second DLT (after reverting to the per protocol schedule) → skip the next GPS inoculation (scheduled for the next cycle, i.e., 3 wks ahead) and administer GPS 6 wks ahead (i.e., 'spread out') **twice thereafter**, i.e. **for 2 additional cycles** → DLT resolution → Return to per protocol schedule of GPS administration

- Third DLT (occurring either after reverting to the per protocol schedule or during the ‘spread out’ schedule to manage the 2nd DLT above) → Discontinue patient from study.
- N.B.: In all above modifications of the dose density of galipepimut-S, as all intervals (in weeks) between 2 successive GPS administrations are multiples of three (3) by design, following these rules, co-administration with pembrolizumab is always secured.

Stopping Rules:

- Development of any SAEs at least “possibly attributable” to the study agent(s) in 2 out of the first 6 patients in the study. In this case, the upper 90% one-sided CI bound for 2 patients with SAEs within 6 patients would be 66.7%, consistent with an excessive rate of toxicity.
- The fraction of patients experiencing an SAE at least “possibly attributable” to the study agent(s) exceeds 1/3, at any time during study implementation beyond the first 6 patients.
- Death at least “possibly attributable” to the study agent(s) within 30 days after the administration of the investigational treatment (GPS plus pembrolizumab).

If the study is stopped due to activation of the above rules, the safety data will be examined by the Sponsor in consultation with investigators in order to determine how to proceed or whether to discontinue the study at large.

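### The per-patient DLT list fixes GPS re-dosing at 6 weeks, which matches the doubling rule it summarizes at only 7 of the 12 GPS intervals from Week 9; the step-2 trigger and the AML starting cycle are also each worded two ways

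*Combined protocol and SAP*

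**What the plan says.** Sections 5.3.6.1 (solid tumours) and 5.3.6.2 (AML) each contain a rule for an individual patient whose DLT arises once the first combination cycle is complete. The rule has no end date. In the prose, "the time interval between galinpepimut-S doses for the inoculation following the one associated with the DLT will be doubled", while pembrolizumab continues unchanged. The synopsis expresses the same step as halving the GPS frequency.

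The protocol says that this modification "is further summarized in the bulleted list of actions below". For a first DLT the list reads "skip the next GPS inoculation (scheduled for the next cycle, i.e., 3 wks ahead) and administer GPS 6 wks ahead"; this is done once, and the patient then returns to the protocol schedule. The list appears four times: in the synopsis for each arm, in 5.3.6.1 and in 5.3.6.2.

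GPS is not 3-weekly throughout. Under Section 3.1.1 and Table 8 there are 6 weeks between the Week 15 and Week 21 doses and 12 weeks between Weeks 36 and 48. GPS then moves to an "every 12-week schedule for 4 additional doses (late immune booster phase; weeks 48-84". In the synopsis, the last GPS "administration would occur at 84 weeks".

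Step 2 calls for two spaced doses. The prose introduces it with "If another DLT occurs in that next cycle" and the list with "Second DLT (after reverting to the per protocol schedule". A third DLT means discontinuation.

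**The concern.** The prose rule is relative, so it stretches whatever interval applies. The list is absolute, and its figures suit only a patient whose next GPS dose is 3 weeks off. The rule remains in force through both booster phases, so the list will also be read at doses where that is not so. There it gives a different date from the prose, and at most of those doses a date before the dose it tells the site to skip.

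At stake is the instruction a site uses to re-dose after a DLT, in a study where safety and tolerability is a primary objective. The two smaller inconsistencies bear on which step applies to a second DLT, and on when the rule begins for an AML patient.

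**Working it through.** **Inputs.** The GPS weeks (Section 3.1.1, Table 8) are 0, 3, 6, 9, 12, 15, 21, 24, 27, 30, 33, 36, 48, 60, 72 and 84, which makes 16 doses. The first co-administration is at Week 6 and cycles last 3 weeks, so combination cycle 1 ends at Week 9 and cycle 2 at Week 12.

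**Formulas.** For a DLT associated with the dose at week *w*, with the next planned dose *d* weeks later:
- prose: next GPS at *w* + 2*d*;
- list: next GPS at *w* + 6.

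**Reproducing the list's figure.** For *d* = 3, 2 × 3 = 6 weeks. The list is therefore right for 3-weekly dosing.

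**All intervals from Week 9.** The 12 intervals are 3, 3, 6, 3, 3, 3, 3, 3, 12, 12, 12 and 12 weeks. Seven are 3 weeks (after Weeks 9, 12, 21, 24, 27, 30 and 33), and there prose and list agree. The other five do not:

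| DLT at week | Next planned dose | *d* | Prose, *w* + 2*d* | List, *w* + 6 | List minus planned |
|---|---|---|---|---|---|
| 15 | 21 | 6 | 27 | 21 | 0 |
| 36 | 48 | 12 | 60 | 42 | −6 |
| 48 | 60 | 12 | 72 | 54 | −6 |
| 60 | 72 | 12 | 84 | 66 | −6 |
| 72 | 84 | 12 | 96 | 78 | −6 |

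After Week 15 the list lands on the planned date, so nothing is delayed. After the other four it lands 6 weeks before the dose that the same line says to skip. Doubling has a gap of its own: after Week 72 it gives Week 96, beyond the last planned GPS dose at Week 84.

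**Step 2.** The prose covers a second DLT during the first spaced cycle. The list covers a second DLT after return to schedule. Both prescribe the same action, two spaced doses, but neither text covers both situations. The list's third-DLT bullet does name both timings, so the narrower second-DLT bullet leaves a gap.

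**AML start.** The synopsis applies the per-patient rule after the second combination cycle (Week 12), and Section 5.3.6.2 after the first (Week 9). The difference is one 3-week GPS interval. Starting at Week 12 leaves 12 − 1 = 11 intervals, of which 7 − 1 = 6 agree; the five that disagree are unchanged.

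**The case against.** The best defence is that the list presupposes a dose 3 weeks away. At the five doses in question no such dose exists, so the premise fails and the prose governs. A careful site could well work this way, and that limits the harm. It does not remove the defect, because the list carries no such restriction. The note beneath it, on GPS intervals being multiples of three weeks, reads as if the rules cover every interval.

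Second, other sections stand between the list and an early dose. Section 5.3.7 requires the medical monitor's involvement before re-challenge after a local grade 3 reaction and for related systemic grade 3 or 4 events. It takes patients off treatment for persistent local toxicity of grade 3 or higher and for non-skin autoimmune or anaphylactic reactions. Section 4.2.2 has the investigator confer with the sponsor on serious or intolerable events. This stands as real mitigation, although neither section states an interval or a step.

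Third, for AML, Section 5.3.6.2 defines DLTs within the first 8 weeks. The same section then applies the per-patient rule to those toxicities at any later time, so the 8-week window does not dispose of the point.

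A reader might also infer that the prose itself is ambiguous, because an example describes GPS that "was given on a Q3W schedule before the DLT occurred, it should be given Q6W for the immediately subsequent administration". Doubling the preceding 3-week schedule would give Weeks 21 and 42 after Weeks 15 and 36, the same as the list. That example belongs to the cohort rule (more than 2 DLTs in a group of 6 patients), and the per-patient rule in these sections has no example. Its wording points most naturally to the forthcoming interval, which gives one date at each dose.

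**Conclusion.** The inconsistency is real and lies in the current text. The list agrees with the rule it summarizes at 7 of 12 GPS intervals from Week 9 and disagrees at 5. At those five, taken literally, it gives no delay once and a dose 6 weeks early four times. These figures assume that the prose doubles the interval from the DLT-associated dose to the next planned dose. They count intervals, not patients; the documents give no basis for estimating how many patients would have a DLT at these doses. The step-2 trigger and the AML start are lesser inconsistencies.

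Three stronger readings are not supported:
- That the protocol intends or would in practice produce faster dosing after toxicity. The same line says to skip a dose, the prose says to double the interval, and Section 5.3.7 intervenes in many cases.
- That sites would take opposite actions at a second DLT. Both step-2 triggers lead to two spaced doses, and the prose's discontinuation sentence most naturally refers to a DLT after both modifications.
- That the trial's results are affected. No endpoint, sample size or Stop/Go boundary depends on this rule.

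The point ranks between minor and should-fix: it concerns a safety instruction, exposure to it is limited, and the correction is cheap.

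**What to change.** Make the same change in all four places (synopsis for both arms, 5.3.6.1 and 5.3.6.2):

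1. Limit the fixed 3-week and 6-week wording to DLTs where the next planned GPS dose is 3 weeks away. The seven dates that now agree stay as they are.
2. For DLTs at Weeks 15, 36, 48, 60 and 72, state that the next planned dose is skipped and GPS is given at twice the interval from the DLT-associated dose to that planned dose, never on or before the skipped date. No GPS is given after Week 84. This yields Weeks 27, 60, 72 and 84, and no further GPS after a Week 72 DLT.
3. State that a second DLT, whether during spacing or after return to schedule, triggers step 2, and define the step-2 interval from the schedule phase in force at that time. The definition must cover off-schedule doses. For example, a DLT at Week 33 puts the step-1 dose at Week 39. After a second DLT there, the step-2 doses could be Weeks 45 and 51 (6-week spacing) or Weeks 57 and 75 (twice the 9 weeks from 39 to 48).
4. Use one starting cycle for the AML rule in the synopsis and in 5.3.6.2.

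The 24-week gaps (2 × 12) and the absence of GPS after a Week 72 DLT are clinical choices for the sponsor to confirm. The cost is rewording by amendment, with no added patients or procedures. A patient with a late DLT may receive fewer GPS doses.

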IgM & IgG antibody (Ab) responses were measured by ELISA against individual WT1 peptides contained within the galinpepimut-S mixture, as well as full length WT1. Immune responders were defined as those with Ab titers going from undetectable to $\geq 1:40$ or ≥ 8 -fold increase if such patients had detectable pretreatment levels. WT1-specific CD4⁺ and CD8⁺ T cell responses were compared to baseline via intracellular cytokine staining flow cytometry and values $\geq 0.6\%$ were considered positive.

Eleven patients with recurrent serous ovarian cancer in their 2nd or 3rd remission were treated on-protocol with the combination of galinpepimut-S and nivolumab. Their baseline demographics and disease characteristics were representative of similar cohorts of patients in

the published literature - mainly by the Gynecologic Oncology Group (GOG) in the US and the Arbeitsgemeinschaft Gynaekologische Onkologie - Studiengruppe Ovarialkarzinom (AGO-OVAR) in Germany. The most common treatment-related AEs with the combination were injection site reaction (maximum [max] grade 1), arthralgia (max grade 2) and fatigue (max grade 2). DLT was observed in one patient, who developed grade 3 panmyositis (including cardiac involvement) following the 2nd dose of galinpepimut-S and nivolumab and required insertion of a permanent cardiac pacemaker. With regard to immune responses, serum levels of antigen-specific IgG, against both individual WT1 peptides within galinpepimut-S and the full-length WT1 protein were induced in 86% of evaluable patients between week 6 and week 27 following treatment with the combination. Antigen-specific T cell responses to individual WT1 peptides were observed between weeks 6-15. These responses were primarily CD4+, with best responses seen against the heteroclitic peptide 122A1-Long and its corresponding native counterpart 122A-Long, and to a lesser extent CD8+, mainly for peptides 427 and 331 in patients with HLA class I allelic types other than HLA-A02.

The landmark PFS rate at 1-year was 64% in the intent-to-treat group as shown in Figure 11 below. The 1-year PFS rate was 70% for patients who received >2 doses of galinpepimut-S and nivolumab.

Figure 11 Study 15-247 (Ovarian Cancer Patients): Kaplan-Meier Plot for Median Progression-Free Survival Showing the Landmark 1-year PFS Rate in the ITT Population

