5.3.6.3. Dose Modification and Toxicity Management Guidelines for Pembrolizumab

5.3.6.3.1. Dose Modification and Toxicity Management for Immune-related AEs (irAEs) Associated with Pembrolizumab

AEs associated with pembrolizumab exposure may represent an immunologic etiology. These immune-related AEs (irAEs) may occur shortly after the first dose or several months after the last dose of pembrolizumab treatment and may affect more than one body system simultaneously. Therefore, early recognition and initiation of treatment is critical to reduce complications. Based on existing clinical trial data, most irAEs were reversible and could be managed with interruptions of pembrolizumab, administration of corticosteroids and/or other supportive care. For suspected irAEs, ensure adequate evaluation to confirm etiology or exclude other causes. Additional procedures or tests such as bronchoscopy, endoscopy, skin biopsy may be included as part of the evaluation. Based on the severity of irAEs, withhold or permanently discontinue pembrolizumab and administer corticosteroids. Dose modification and toxicity management guidelines for irAEs associated with pembrolizumab are provided in [Table 5](#).

Table 5 Dose Modification and Toxicity Management Guidelines for Immune-related AEs Associated with Pembrolizumab

General instructions:
 
 1. Corticosteroid taper should be initiated upon AE improving to Grade 1 or less and continue to taper over at least 4 weeks. 2. For situations where pembrolizumab has been withheld, pembrolizumab can be resumed after AE has been reduced to Grade 1 or 0 and corticosteroid has been tapered. Pembrolizumab should be permanently discontinued if AE does not resolve within 12 weeks of last dose or corticosteroids cannot be reduced to ≤ 10 mg prednisone or equivalent per day within 12 weeks. 3. For severe and life-threatening irAEs, IV corticosteroid should be initiated first followed by oral steroid. Other immunosuppressive treatment should be initiated if irAEs cannot be controlled by corticosteroids. 				
Immune-related AEs	Toxicity grade or conditions (CTCAEv5.0)	Action taken to pembrolizumab	irAE management with corticosteroid and/or other therapies	Monitor and follow-up

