6.1.4. Safety Follow-up Period

Patients who complete the study treatment period or discontinue early (if they have received at least 1 treatment injection) will enter an off-treatment follow-up period to assess progression-free survival and overall survival. A follow-up telephone call for serious adverse events will occur 90 days after the last dose of pembrolizumab or 30 days following cessation of study treatment if the patient begins new anticancer therapy, whichever is

earlier. If the patient initiates new anticancer therapy, this must be reported by the investigator. Patients will be followed in accordance with standard guidelines, which suggest regular assessments every 3 months until study closure, defined as up to 2 years and 6 weeks, i.e., 111 weeks, after the first galipepimut-S administration given to the last patient enrolled into the study (which corresponds to up to 2 years after the first injection of pembrolizumab).

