6.4.1.2. Eliciting and Documenting Adverse Events

Adverse events will be assessed from the time the patient signs the ICF until 30 days after the last study treatment injection. Adverse events collected before injection of study treatment will be reported as pretreatment AEs and those collected after the first injection of GM-CSF and throughout the study will be reported as TEAEs. Serious AEs that occur more than 30 days after the last dose of study treatment need not be reported unless the investigator considers them related to study treatment. Any medical condition that is present at the time that the patient is screened but does not deteriorate should not be reported as an AE. However, if it deteriorates at any time during the study, it should be recorded as an AE.

At every study visit, patients will be asked a standard nonleading question to elicit any medically related changes in their well-being. They will be asked if they have been hospitalized, had any accidents, used any new medications, or changed concomitant medication regimens (both prescription and over-the-counter medications) or therapies. Patients will also be instructed to contact the investigator at any time after beginning study treatment if any signs or symptoms develop.

In addition to patient observations, AEs identified from any study data (e.g., laboratory values), or identified from review of other documents that are relevant to patient safety will be documented on the AE page in the eCRF.

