10.1. External Data Monitoring Committee

Not applicable.

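### The only stopping rule that one related death can trigger lapses 30 days after dosing, although the protocol says immune-related events may arise months after the last pembrolizumab dose

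*Combined protocol and SAP*

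**What the plan says.** The stopping rules appear in four places: the Synopsis (once for the solid tumor arms, once for the AML arm), Section 5.3.6.1 (solid tumors) and Section 5.3.6.2 (AML). The death rule is in substance the same in all four. It requires that the death be at least possibly attributable to the study agents, and that it occur "within 30 days after the administration of the investigational treatment (GPS plus pembrolizumab". One such death is enough.

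The other rules in these lists are defined by attribution or event type and carry no number of days:
- a related SAE in 2 of the first 6 patients;
- a fraction of patients with a related SAE that "exceeds 1/3, at any time during study implementation beyond the first 6 patients";
- AML only: colitis/diarrhea, pneumonitis, nephritis or transaminitis of grade 3 or higher, or myocarditis of any grade, in 2 of the first 6 AML patients, or in more than 40% after that.

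Separately, both sections stop the study if dose-limiting toxicities (DLTs) stay above 2 per 6 patients after patient 12. Grade 5 toxicity is a listed DLT.

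On timing, Section 5.3.6.3.1 says that irAEs "may occur shortly after the first dose or several months after the last dose of pembrolizumab treatment". Table 5 allows a long hold: "Pembrolizumab should be permanently discontinued if AE does not resolve within 12 weeks of last dose". Section 6.1.4 states: "A follow-up telephone call for serious adverse events will occur 90 days after the last dose of pembrolizumab". That call moves to 30 days after cessation if new anticancer therapy begins earlier. Under Section 6.4.1.2, SAEs more than 30 days after the last dose "need not be reported unless the investigator considers them related to study treatment". Sections 6.5 and 10.1 mark a safety monitoring committee and an external data monitoring committee as not applicable.

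**The concern.** A rule that reacts to one related death exists to catch rare, severe harm that a rate rule is too slow to see. Here it is the only rule of that kind, and the only entry in the stopping lists with a day limit.

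The limit also tends to expire in the patients for whom the rule matters. While dosing is on schedule, a dose falls every 3 weeks, so 30 days never run out if any dose restarts the clock. Table 5, however, requires permanent discontinuation of pembrolizumab for grade 3 or 4 pneumonitis, myocarditis, nephritis and hepatic events. Managing a dangerous irAE can therefore end the dosing that would have renewed the window. If that patient dies of the event on day 45, the rule does not apply.

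The parenthesis in the rule also leaves open which dose starts the clock: any dose of the regimen, or only a visit at which both drugs are given. With no independent committee, the written rules are the only automatic protection.

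**Working it through.** **The plan's own figure.** The only number given with the stopping rules is an upper one-sided 90% bound of 66.7% for 2 SAE patients in 6. The exact bound is the 0.90 quantile of Beta(3, 4) = 0.6668, so it reproduces. It concerns the SAE rule. The death rule has no calculated figure.

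**Does any other rule react to one late related death?** A death is an SAE (Section 6.4.1.1), so it counts as one patient.
- First 6 patients: 1 of 6, and 2 are needed. The second may be any related SAE, fatal or not.
- Later, the smallest count above 1/3 is floor(n/3) + 1: 3 of 7, 7 of 20, 31 of 90. One death is 1/7 = 14% at n = 7 and 1/90 = 1.1% at n = 90.
- AML irAE rules, if the death comes from a listed event: 2 of the first 6, then floor(0.4n) + 1, which is 3 of 7 or 7 of 15.
- DLT rule, if the death qualifies as a DLT: one of the more than 2 in 6 that are needed. The first response is a longer galinpepimut-S interval, and a study stop comes only after patient 12.

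None is met by one death alone.

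**How much time is uncovered?** Take the reading most favourable to the plan (any dose starts the clock, day 30 included), with no new anticancer therapy. Days 31 to 90 after the last dose are 60 days, and 60/90 = 67% of the SAE follow-up. As a share of the time from first dose to day 90 after the last dose, 60/(7 × week of last dose + 90):

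| Last dose | Days | Share uncovered |
|---|---|---|
| Week 6 | 60/132 | 45% |
| Week 18 | 60/216 | 28% |
| Week 36 | 60/342 | 18% |
| Week 108 | 60/846 | 7% |

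These are upper bounds. A patient who starts new therapy has the SAE call at 30 days and contributes little or none of the 60 days.

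During a 12-week pembrolizumab hold with no other dose, days 31 to 84 are uncovered: 54/84 = 64%. A galinpepimut-S dose inside the hold would shorten this, and galinpepimut-S is scheduled every 21 days through Week 36, with one 42-day gap.

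**If only co-administration starts the clock.** Co-doses fall at Weeks 6, 9, 12, 15, 21 to 36 (every 3 weeks), 48, 60, 72 and 84. Days more than 30 after the latest co-dose, Weeks 6 to 111: 11 (Weeks 15 to 21) + 4 × 53 (the four 84-day gaps) + 159 (after Week 84) = 382 of 736 days.

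**Illustration only.** The documents give no rate of related death on days 31 to 90. Assume a per-patient risk p, with all 90 patients exposed for all 60 days. The chance of at least one such death is 1 − (1 − p)^90: 36% at p = 0.5%, 60% at 1%, 84% at 2%. If only half the patients were exposed (also an assumption), 1 − (1 − p)^45 gives 20%, 36% and 60%.

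**The case against.** The strongest reply is that little is lost in practice. A triggered rule leads to a safety review by the sponsor with the investigators. The sponsor already hears of every death immediately (Section 6.4.1.3), receives related SAEs after day 30 (Section 6.4.1.2) and may stop at any time (Sections 4.2.1 and 10.4). Thirty days also matches routine adverse event collection (Section 6.4.1), so the limit is a coherent choice. And the lowest related category, possible, admits events that other factors could explain (Section 6.4.1.5). In advanced cancer, a single such attribution would pause a five-cohort study.

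Much of this stands. The loss is the automatic pause, not knowledge of the death, and the pause has a price. It does not rescue the limit itself: Section 6.4.1.2 already makes an exception to 30 days for related SAEs, and the neighbouring rules accept possible attribution without any day limit.

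A reader might also infer that late immune-related deaths have been seen with this combination. The documents do not show that. In Study 15-247, 1 of 11 patients had "grade 3 panmyositis (including cardiac involvement) following the 2nd dose of galinpepimut-S and nivolumab". It was counted as a DLT, which in that study had to occur within 30 days of the first galinpepimut-S dose, and it was not fatal. It shows that serious irAEs occur, not that late deaths do.

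**Conclusion.** The point holds as a gap in one rule. A death judged possibly related after day 30 cannot trigger the only single-death rule, and no other rule fires on that death alone.

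Three stronger readings are not supported:
- That such a death escapes all stopping rules. It counts as one patient toward the SAE rules, and toward the AML irAE or DLT rules where it qualifies.
- That the protocol expects late irAEs. It says only that they may occur.
- That 67%, or the 36% to 84% range, measures the risk. The first is a share of calendar days and an upper bound. The second rests on assumed rates and on full exposure of all 90 patients.

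The 382 of 736 days depend on the co-administration reading, which the wording allows but does not settle. The size of the gap in patients is unknown, because the documents give no late-death rate. This is a cheap improvement to patient protection, not a flaw that undermines the design.

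**What to change.** In all four places (both Synopsis lists, Sections 5.3.6.1 and 5.3.6.2), delete the 30-day window and let attribution decide, as the SAE rules do. At minimum, replace it with: within 90 days after the last dose of either galinpepimut-S or pembrolizumab, or 30 days if new anticancer therapy has begun. This fallback names the dose that starts the clock and stays close to Section 6.1.4, whose 90 days run from pembrolizumab only. It would still miss a related death after day 90, so deletion is the better choice.

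The cost is one phrase in four places, with an amendment and IRB approval (Section 10.3.1). No new data are needed, because all deaths and late related SAEs are already reported. Attribution continues to exclude deaths judged unrelated, such as those from the cancer alone. The downside is an occasional pause and sponsor review for a late death judged only possibly related.
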